#### mRNA and microRNA Expression

Total RNA will be isolated from approximately 25 mg of muscle using a mirVana™ miRNA isolation kit (Invitrogen, Carlsbad, CA, USA) or equivalent. Quantity and quality of RNA will be assessed using a Nanodrop ND-1000 spectrophotometer (Nanodrop, Wilmington, DE, USA) or equivalent. Equal amounts of total RNA will be synthesized into cDNA for analysis of mRNA (High-Capacity cDNA RT Kit, Applied Biosystems, Foster City, CA, USA or equivalent) and a TaqMan® microRNA RT kit (Applied Biosystems) or equivalent. Individual primers will be used to determine the mRNA expression of known intracellular targets regulating protein metabolism, to include but not limited to atrogen, MurF-1, LARS, LAT1, SNAT2, REDD1, and IGF1. Individual primers will be used to determine microRNA expression of microRNA that have been reported to impact skeletal muscle anabolism, to include but not limited to miR-1, miR-133a/b, miR-206, miR-208, miR-486, and miR-499

To determine if circulating microRNA reflect changes within skeletal muscle to exercise and dietary protein intake total circulating microRNA will be extracted from 200  $\mu$ L serum using miRNeasy Serum/Plasma kit or equivalent, which allows for extraction and purification of small (< 200 nt) cell-free RNA (Qiagen, Valencia, CA, USA). Additionally, to assess if changes in circulating microRNA differ between total and exosomal circulating microRNA, exosomes will be extracted from 1000  $\mu$ L serum using a miRCURY™ Exosome Isolation Kit-Serum and Plasma (Exiqon, Woburn, MA) or equivalents. To avoid introduction of potentially contaminating material, prior to RNA extraction serum samples will be centrifuged for 10 min at 4°C to remove cellular debris. Supernatant will be removed and transferred to a new tube without disturbing the pellet. Due to the small amount of RNA in the serum, 3.5  $\mu$ L of a Spike-In Control (C. elegans miR-39; Qiagen) will be added to all samples prior to extraction of RNA to determine the yield of template recovered. After extraction 3  $\mu$ L of serum RNA will reverse transcribed using the TaqMan® microRNA RT kit (Applied Biosystems) or equivalent with miRNA-specific stem-loop RT primers pooled in 1X-Tris-EDTA (TE) buffer for a final dilution of 0.05X. A pre-amplification step will be performed after reverse transcription to increase cDNA template using a primer pool of 20 X Taqman® Small RNA Assays (Applied Biosystems) or equivalent for miRNA of interest at 0.05X concentration in 1X TE buffer. All serum miRNA will be normalized to the geometric of external (Spike-In Control C. elegans miR-39) and internal controls to allow for both technical and inter-individual normalization. Geometric mean of controls will be used to correct for possible outlying values and abundance differences between the different controls [52].

All reverse transcription for mRNA and miRNA, and pre-amplification of serum miRNA will be conducted in a T100™ Thermal Cycler (Bio-Rad, Hercules, CA or similar model). A StepOnePlus™ real-time PCR system

(Applied Biosystems or similar model) will be used to perform all mRNA and miRNA analysis. Fold changes will be calculated using the  $\Delta\Delta$  cycle threshold ( $\Delta\Delta C_T$ ) method as described below in statistical analysis section.

### Western Blotting

Approximately 30 mg of muscle will be homogenized in ice-cold buffer (1:10 wt/vol) containing 50 mM Tris-HCl (pH 7.5), 5 mM Na-pyrophosphate, 50 mM NaF, 1 mM EDTA, 1 mM EGTA, 10% glycerol (v/v), 1% Triton-X, 1 mM DTT, 1 mM benz-amidine, 1 mM PMSF, 10  $\mu$ g mL trypsin inhibitor and 2  $\mu$ g mL aprotinin. Homogenate will be centrifuged for 15 min at 10,000  $\times$  g at 4°C. Protein concentration of supernatant (lysate) will be determined using 660 nm Protein Assay (ThermoFisher Scientific, Waltham, MA, USA or equivalent). Phosphorylation status and total protein expression of molecular markers associated with anabolism will be determined using Western blotting techniques. Muscle lysates will be solubilized in Laemmli buffer, with equal amounts of total protein (15  $\mu$ g) separated by SDS-PAGE using precast Tris-HCl gels (Bio-Rad). Proteins will be transferred to polyvinylidene fluoride (PVDF) membranes and exposed to commercially available primary antibodies of intracellular markers involved with skeletal muscle anabolism and proteolysis to include but not limited to Akt, p-AktSer473, mTOR, p- mTORThr2448, p70S6K, p-p70S6KThr424, rpS6, and rpS6Ser235/236 (Cell Signaling Technology, Danvers, MA, USA or equivalent) at 4°C overnight. Labeling will be performed using secondary antibody (anti-rabbit IgG conjugate with horseradish peroxidase; Cell Signaling Technology), and chemiluminescent reagent will be applied (Super Signal, West Pico Kit; Pierce Biotechnology, Rockford, IL, USA). Blots will be quantified using a phosphoimager (ChemiDoc XRS; Bio-Rad) and Image Lab software (Bio-Rad) or similar models. To confirm equal protein loading per well a normalizing protein such as GAPDH or HSP90 will be assessed.

## **B5.5 Managing Data and/or Human Biological Specimens for this Research**

All data and medical information obtained will be considered privileged and held in confidence. Study volunteers will be assigned unique subject identification (ID) numbers that will not contain any personal identifiers such as name, social security number, address, date of birth, zip code, etc. This study subject ID number will be used on all data collection instruments, to include questionnaires, data collection forms, computer records, etc. (**Appendices A - D**). A number will be assigned as each volunteer is enrolled for participation. A master list linking the volunteers' names and ID numbers will be kept in a separate locked file in the principal investigator's or the project coordinator's office, or kept in a computer file with password-protected access restricted to the principal investigator and the project coordinator. Social security numbers and banking information will be collected to process volunteer payments. The master list link, social security numbers, and banking information will be deleted immediately after the study has been completed and payment has been confirmed. When the results of the research are published or discussed in conferences, no information will be included that would reveal identity. Study samples will be processed on site at USARIEM and stored in Military Nutrition laboratory freezers (room 322, 304) using the subject identification number indefinitely for reanalysis if necessary. Coded study samples (blood and muscle) for isotopic and amino acid analysis will be shipped on dry ice to [name] at UAMS via FedEx and stored in his laboratory until analyzed. Once analyzed, there will be no remaining sample for storage.

Only personnel assigned to the research study by the principal investigator will have access to the data. Only the principal investigator and project coordinator will have access to personal identifiable data. Hard copy data records will be stored for a minimum of three years from the time the study is completed. Electronic data records will be maintained for a period of at least ten years after the study has been completed.

## **B5.6 Managing Data and/or Human Biological Specimens for Future Research**

Any use of the samples outside of this defined protocol will be submitted as a protocol amendment or a new protocol. Samples will be retained for further analyses related to metabolic biomarkers sensitive to EAA, resistance exercise, and energy deficit once the protocol is closed. Participants will be made aware of this during the informed consent process.

## **B5.7 Devices, Drugs, Dietary Supplements, Nutritional Supplements, And Biologics**

### **B5.7.1 Devices**

#### **5.7.1.1 FDA-approved device being used in this research according to the approved labeling**

**DEXA, DPX-IQ, Lunar Corporation, Madison, WI**

#### **5.7.1.2 FDA-approved device being used in this research in a manner other than its approved labeling**

N/A

### **B5.7.2 Drugs**

#### **B5.7.2.1 FDA-approved and used in accordance with the approved labeling**

N/A

#### **B5.7.2.2 FDA-approved and used in a manner not in accordance with its approved labeling**

N/A

#### **B5.7.2.3 Any drug not approved by the FDA**

N/A

## **B5.8 Statistical Analysis**

### **B5.8.1 Sample Size Estimation**

Means (SD) from Macnaughton et al. [53] and Witard et al. [9] demonstrating the effects of graded protein dose on resting and post-resistance exercise muscle FSR were used to determine statistical power and sample size. Using those data, we anticipate observing a mean (SD) difference in muscle FSR of ~0.015 %/h (0.02 %/h) for both the rested and exercised leg between EAA doses. The sample size necessary to determine differences between EAA doses (assuming an alpha of 0.05, mean difference of 0.015 %/h, standard deviation of 0.02 %/h, and 80% power) is 16. However, 20 volunteers will be studied to account for the potential for greater variability than those reported by others and to increase our statistical power to 90% in order to detect differences between the 0.10 g/kg and 0.3 g/kg EAA doses. This estimate also provides greater than 95% power to detect differences in whole-body protein balance between EAA doses [16]. We request the ability to increase our enrollment to 40 volunteers to account for screening failures and study attrition. Enrollment and testing will cease once data has been collected on 20 volunteers.

### **B5.8.2 Data analysis**

Statistical analyses will be conducted using either SPSS (IBM Corp. Armonk, NY), SAS 9.3 (SAS Institute Inc., Carey, NC), or equivalent. Common descriptive statistics will be used to describe volunteer characteristics. Shapiro-Wilk tests will be used to determine normality of data. An ANOVA will be performed to determine the effects of EAA dose (0.10 g/kg vs. 0.3 g/kg) on muscle FSR and whole-body protein turnover. Correlation coefficients and multiple regression analysis will be used to evaluate relationships between study outcome measures. The alpha level will be adjusted for multiple comparisons, with the level for statistical significance set at  $P < 0.05$ .

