#### **B5. RESEARCH PLAN**

##### **B5.1 Research Design**

This study will be a randomized, double-blind, cross-over controlled trial. Before the study begins, a research team member ([name]) will generate the randomization scheme using a random number generator (<http://randomization.com>). [name] will be responsible for preparing and coding the individualized EAA drinks for each trial and she will hold the randomization code until the study has been completed (i.e., data collected and analyzed). The study investigators will be blinded to this process. The code will be broken by [name] after the primary outcomes (i.e., muscle protein synthesis and whole-body protein balance) have been statistically analyzed by the study investigators (i.e., [name], [name], [name], [name], [name], and [name]).

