## **B5.3 Research Procedures**

### **Experimental Design**

[figure not shown]
Twenty resistance-trained adults will be tested in this approximately 39-d randomized, double-blind cross-over study. Volunteers will participate in two, non-consecutive 5-d controlled energy deficit periods, separated by a 14-d washout period (i.e., sufficient time to restore nitrogen and metabolic homeostasis after moderate weight loss) [35-38]. Basal (fasting/resting), resting and post-resistance exercise (single leg exercise model) whole-body protein turnover and skeletal muscle protein synthesis responses to standard (0.10 g/kg) and high (0.30 g/kg) EAA doses will be determined the morning after completing each 5-d energy deficit. To limit potential confounding effects of pre-study diet, and to be consistent with our previous research [16, 39, 40], volunteers will be provided a 3-d run-in, eucaloric diet. After the 3-d eucaloric run-in diet, energy intake will be reduced by 30%. Physical activity will be completely restricted during the 3-d run-in diet and 5-d energy deficit to isolate the effects of the energy deficit on protein turnover and limit any residual effects of previous exercise on outcome measures [41].

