At 120-min, a muscle biopsy of the vastus lateralis will be taken on the non-exercised leg only to assess basal (fasting/resting) muscle protein kinetics. After the muscle biopsy, volunteers will remain rested until they perform a heavy-load, high volume, single leg-resistance exercise bout at 195-min that consists of 8 sets X 10 repetitions on the leg-press and leg-extension machines [9]. Both exercises will be performed at 80% of a pre-determined one repetition maximum (1RM) with a 2-min rest interval between sets. Volunteers will have ~45-min to complete the exercise bout. In the event the volunteer is unable to complete the prescribed workload; the workload will be reduced by 4.5 kg as previously described [9]. This will be repeated until the participant can complete the prescribed work. Approximately 5-min after completing the exercise bout (240-min), a muscle biopsy will be taken from the vastus lateralis of the exercised and non-exercised (rested) legs (the exercised and non-exercised leg will be the same between trials). Immediately after the biopsies, volunteers will consume the appropriate dose (i.e., an artificially flavored beverage) of free-form EAA in 5-10-min [Reginator™; EAA content per 10 g of the mixture: 0.15 g histidine, 3.66 g leucine, 0.94 g isoleucine, 1.65 g lysine, 0.3 g methionine, 0.63 g phenylalanine, 0.89 g threonine, 0.1 g valine, 0.006 g tryptophan, and 0.81 g arginine (conditionally essential under stress)]. The phenylalanine content of the beverage will be artificially

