### **Anthropometric Data**

Anthropometrics, performed using standardized techniques and equipment, will be used to characterize study volunteers, and evaluate responses to each 5-d energy deficit. Height will be measured in duplicate to the nearest 0.1 cm using a stadiometer at baseline. Body weight will be measured, nude (scale will be placed in a locked bathroom) and after an overnight fast ( $\geq 8$  h), using a calibrated digital scale to the nearest 0.1 kg at baseline and then daily during each 3-d run-in and 5-d energy deficit period to ensure weight maintenance and/or weight loss. Body mass will be measured every third day during the 14-d washout period (measurements will correspond with the days diet records and activity logs are reviewed described above).

Body composition will be determined at baseline and after the 14-d washout by using a dual energy x-ray absorptiometry (DEXA, DPX-IQ, GE Lunar Corporation, Madison, WI). The DEXA technique allows for the non-invasive assessment of soft tissue composition by region with a precision of 1-3%. The volunteer will lay face-up on the DEXA densitometer table in shorts, t-shirts, and stocking feet, and will be asked to remain motionless for the 8-10 min scan. These data will be used to calculate total body mass, fat-free mass, and fat mass. Calibration to external standards will be performed before actual data collection. The operator remains in the room with the volunteer during the scan.

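### B5.8.2 names dose as the only ANOVA factor for a two-period cross-over: it should state a within-volunteer comparison with a period term

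*Combined protocol and SAP*

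**What the plan says.** B5.1 sets the design: "This study will be a randomized, double-blind, cross-over controlled trial". On the allocation of dose order it says only that a team member "will generate the randomization scheme using a random number generator" before the study begins. It does not say whether the two orders are balanced.

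Under Experimental Design in B5.3: "Volunteers will participate in two, non-consecutive 5-d controlled energy deficit periods, separated by a 14-d washout period". Leg assignment is fixed: "the exercised and non-exercised leg will be the same between trials".

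B5.8.1 sizes the trial on a difference between doses: "we anticipate observing a mean (SD) difference in muscle FSR of ~0.015 %/h (0.02 %/h) for both the rested and exercised leg". It gives 16 volunteers for 80% power and 20 for 90%, and adds: "Enrollment and testing will cease once data has been collected on 20 volunteers".

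B5.8.2 gives the dose comparison one sentence: "An ANOVA will be performed to determine the effects of EAA dose (0.10 g/kg vs. 0.3 g/kg) on muscle FSR and whole-body protein turnover". Neither that section nor any other part of the documents names a volunteer effect, pairing, repeated measures, a mixed model, period or order for the analysis.

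**The concern.** In a cross-over, each volunteer is measured under both doses at two different times. A model with dose alone leaves two things open: whether the doses are compared within volunteer, and what happens to any general change between the first trial and the second.

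The second matters more. Volunteers reach the second trial after a first energy deficit and a first biopsy session and, for the exercised leg, after a heavy bout on that same leg. If second-trial values differ systematically from first-trial values, a paired analysis without period puts that shift into the error variance and loses power. If the two orders are also unequal among the 20 volunteers analysed, part of the shift enters the dose estimate.

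**Working it through.** **Inputs from B5.8.1:** difference d = 0.015 %/h, SD of the difference s = 0.02 %/h, alpha 0.05 (taken as two-sided), n = 16 and n = 20.

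**Assumed, not in the documents:** a shift k of 0.005 or 0.01 %/h between trials, order splits of 10:10, 12:8 and 14:6, and, for the averages, order drawn by an unrestricted coin toss.

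**1. The plan's own figure.** Paired t-test, noncentrality (d/s) × √n, n − 1 degrees of freedom.
- n = 16: 0.75 × √16 = 3.00, power 80.1% (n = 15 gives 77.1%).
- n = 20: 0.75 × √20 = 3.35, power 88.9%.

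So 16 reproduces exactly and 90% at n = 20 is close. A two-sample t-test with an SD of 0.02 per dose would need 29 per group and would have 64% power with 20 per group. The sample size was therefore built on a within-volunteer comparison.

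**2. Paired analysis without period.** A volunteer's high-minus-low difference has mean d + k if the high dose comes second and d − k if it comes first. With n1 and n2 volunteers in the two orders:
- bias of the dose estimate, given the split = k × (n1 − n2)/20
- added sum of squares in the error = k² × 4 × n1 × n2/20

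Power and type I error come from exact integration over a normal mean and a noncentral chi-square variance on 19 degrees of freedom.

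| Split | Shift k (%/h) | Bias (%/h) | Power | Type I error |
|---|---|---|---|---|
| 10:10 | 0 | 0 | 88.9% | 5.0% |
| 10:10 | 0.005 | 0 | 87.6% | 4.4% |
| 10:10 | 0.01 | 0 | 83.3% | 2.9% |
| 12:8 | 0.005 | 0.005 × 4/20 = 0.001 | 82.8% or 91.4% | 4.9% |
| 12:8 | 0.01 | 0.01 × 4/20 = 0.002 | 71.1% or 91.8% | 4.5% |
| 14:6 | 0.005 | 0.005 × 8/20 = 0.002 | – | 6.4% |
| 14:6 | 0.01 | 0.01 × 8/20 = 0.004 | – | 9.7% |

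The two powers at 12:8 are for a bias against and in favour of the high dose. Relative to d, the 12:8 biases are 0.001/0.015 = 7% and 0.002/0.015 = 13%.

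**3. Paired analysis with period.** 18 degrees of freedom and an effective n of 4 × n1 × n2/20. The shift drops out.
- 10:10: effective n = 20, power 88.7%.
- 12:8: effective n = 19.2, power 87.4%.

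Type I error is 5% at any split.

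**4. Averaged over unrestricted random orders (binomial, 20 volunteers, probability 0.5).**

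| Shift k (%/h) | Power without period | Power with period |
|---|---|---|
| 0 | 88.9% | 86.9% |
| 0.005 | 87.0% | 86.9% |
| 0.01 | 81.2% | 86.9% |

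Without period, the average bias is zero and type I error averages 5.0%. The period term breaks even at a shift of about 0.005 %/h here, and at 0.0019 %/h if the orders are exactly 10:10.

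**The case against.** The strongest reply is that the harm rests on assumptions. The documents give no estimate of a shift, and the values used are a third and two thirds of the planned effect. The design works against one: a 14-day washout, a repeated run-in diet and new incisions for the second trial. The first exercise bout does not load the rested leg at all. The plan does track change across the washout ("Body composition will be determined at baseline and after the 14-d washout"), but that is monitoring of body composition, not evidence that FSR or protein balance moves. All of this stands, and it limits the severity.

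The period term is also not free. If orders are unbalanced and the shift is below about 0.005 %/h, it loses a little power on average. That stands too. Unequal orders are themselves inferred from silence in B5.1; the randomization scheme may be balanced. Even a balanced list can end unequal, because testing stops at 20 volunteers with data and some may drop out.

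Two stronger readings are tempting. A reader might infer that an unpaired ANOVA is planned. The documents do not support this, because the sample size in B5.8.1 works only as a paired calculation. A reader might also infer that leaving out period makes the trial biased or inflates its type I error in general. It does not: both effects are conditional on an unequal realised split, and over random orders the estimate is unbiased and type I error averages 5.0%. At 10:10 and 12:8 with the shifts used here, type I error stays below 5%.

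**Conclusion.** The point holds as an under-specification with a cheap remedy. B5.8.2 does not state the within-volunteer comparison that B5.8.1 relies on, and no period term is planned. The cost of the omission depends on a shift that the documents do not quantify. At 10:10 it is 88.9 − 87.6 = 1.3 points of power at 0.005 %/h and 88.9 − 83.3 = 5.6 points at 0.01 %/h. With unequal orders, a bias conditional on the split is added, and at 14:6 the conditional type I error reaches 6.4% or 9.7%.

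All powers use alpha 0.05 without adjustment. B5.8.2 says alpha will be adjusted for multiple comparisons but names no method, so power in the planned tests may be lower; at an assumed 0.025 and 10:10 it is 81.2% without period (no shift) and 80.9% with it. Nothing here puts the validity of the trial or the choice of 20 volunteers in doubt. Severity is modest.

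**What to change.** State in B5.8.2 that the dose effect is estimated within volunteer with a period term, that is, as the high-minus-low difference adjusted for the order in which the doses were given. State it separately for rested-leg FSR, exercised-leg FSR and whole-body protein balance.

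The cost is a sentence of text and one degree of freedom. It needs no new data and no more volunteers. If there is no shift, power at n = 20 goes from 88.9% to 88.7% with 10:10 orders, to 87.4% at 12:8, or to 86.9% averaged over unrestricted orders.

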The 30% energy deficit from diet alone is consistent with our previous energy deficit studies [42] and work demonstrating that a 10-d, 20% diet-induced energy deficit (i.e., ~500 kcal/d) downregulates resting skeletal muscle protein synthesis by as much as 19% [43]. Others have shown that 5-d of moderate energy deficit (reducing energy availability from 50 kcal/kg fat-free mass to 30 kcal/kg fat-free mass) is long enough to downregulate resting skeletal muscle protein synthesis by 27% [35]. In that study, ingesting 15 g and 30 g of whey protein isolate after a bout of resistance exercise restored muscle protein synthesis rates to resting, fasting rates observed during energy balance in a dose dependent manner. This proposal will extend these findings and determine if the observed muscle protein synthetic plateau after conventional resistance exercise [9] during energy balance persists during moderate energy deficit when EAA are ingested relative to body mass (0.10 g/kg versus 0.30 g/kg). Relative EAA intakes were chosen to minimize inter-subject variability and to provide a spectrum of responses to varying absolute EAA doses in order to delineate the breakpoint, and practical dose, at which skeletal muscle and whole-body anabolic responses are optimal [44]. This study will be the first to assess whole-body protein kinetics in response to consuming different doses of EAA and their associations with muscle protein synthesis during short-term energy deficit.

The stable isotope infusion protocol will occur in the morning following an overnight fast (**Figure 6**). Two intravenous catheters will be placed; one for the infusion of stable isotopes, and the other heated for serial “arterialized” blood sampling. As previously described [45], a baseline blood sample will be drawn (0-min) prior to primed continuous infusions of L-[ring-H5]-phenylalanine and L-[3,3-H2]-tyrosine. To appropriately reach isotopic equilibrium of L-[ring-H4] tyrosine enrichment derived from L-[ring-H5]-phenylalanine tracer, a priming dose of L-[ring-H4]-tyrosine also will be injected at 0-min [45]. All isotopes will be purchased from Cambridge Isotope Laboratories (CIL, Andover, MA) and solutions will be constituted by a licensed pharmacy and certified sterile and pyrogen free before administration (pharmacy to be determined).

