**Figure 6. Infusion Protocol**

enriched with L-[ring-H5]-phenylalanine to 4% to limit potential disturbances in isotopic steady-state. Volunteers will remain rested during serial blood sampling over a 3-h period following ingestion. Final biopsies will be taken from each leg at the end of the 3-h period. There will be a total of 2 incisions per EAA trial, one on the rested leg and one on the exercised leg. A total of 5 muscle biopsies will be collected from each volunteer per EAA trial; 2 through 1 incision on the exercised leg and 3 through 1 incision on the rested leg (2 new incisions will be made on the subsequent EAA trial. The incisions on EAA trial 1 will NOT be used for trial 2). Blood samples will be collected at regular intervals to assess isotopic enrichments for kinetic calculations, insulin, blood urea nitrogen, and amino acid concentrations (**Figure 6**).

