#### **Whole-body Protein Turnover and Muscle Fractional Synthesis Calculations**

Calculations of whole-body protein synthesis (PS) and protein breakdown (PB) rates will be performed based on the determinations of the rate of appearance (Ra) into the plasma of phenylalanine and tyrosine and the fractional Ra of endogenous tyrosine converted from phenylalanine [48]. Plasma enrichments of phenylalanine and tyrosine tracers will be curve-fitted with a cubic spline method using Graphpad Prism 5 (Graphpad Software, La Jolla, CA or equivalent). Whole body protein turnover will be calculated by dividing kinetic values of a single essential amino acid (i.e., phenylalanine), which cannot be synthesized in the body, by its fractional contribution to protein. For the calculations for whole-body PB rate, contribution from exogenous EAA and tracers infused will be subtracted from total Ra. Appropriate skew correction will be made for  $^{13}\text{C}$ -labeled tracers [48].

Calculation of resting and post-exercise muscle FSR will be determined as the incorporation of the phenylalanine tracer from biopsy one (180 min) to biopsy two (420 min) using the precursor-product model [49].

The following equations will be used for calculations of whole-body and muscle protein kinetics:

$$\text{Total plasma } R_a = F/E$$

$$\text{Fractional } R_a \text{ of Tyr from Phe} = E_{\text{Tyr M+4}}/E_{\text{Phe M+5}}$$

$$\text{Phe hydroxylation} = \text{fractional } R_a \text{ of Tyr from Phe} \times R_{a|\text{Tyr}}$$

$$PS = [(R_{a|Phe} - \text{Phe hydroxylation}) \times 25]$$

$$PB = [(R_{a|Phe} - F_{Phe}) \times 25 - PRO_{MEAL}]$$

$$NB = PS - PB$$

$$FSR (\%) = [(E_{p2} - E_{p1}) / (E_m \times t)] \times 60 \times 100$$

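### The plan for relating whole-body to muscle outcomes does not say how dose, leg and volunteer are handled; if rows are pooled over doses, false associations become common

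*Combined protocol and SAP*

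**What the plan says.** The analysis of associations is a single sentence in B5.8.2: "Correlation coefficients and multiple regression analysis will be used to evaluate relationships between study outcome measures". The dose effect is covered separately, by an ANOVA. Nothing states which outcomes are paired, whether a row is a volunteer, a trial or a leg, or whether dose, leg, period or volunteer enters the correlation or regression.

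The design fixes the data structure:

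- Two trials per volunteer (B5.3, Experimental Design): "Volunteers will participate in two, non-consecutive 5-d controlled energy deficit periods, separated by a 14-d washout period".
- Two legs per trial (B5.3, text at Figure 6): "2 through 1 incision on the exercised leg and 3 through 1 incision on the rested leg".
- One whole-body value per trial, because the kinetics are derived (B5.4) from "the rate of appearance (Ra) into the plasma of phenylalanine and tyrosine".
- Twenty volunteers (B5.8.1): "Enrollment and testing will cease once data has been collected on 20 volunteers".

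The Experimental Design text says the study will be the first to assess whole-body kinetics at different EAA doses "and their associations with muscle protein synthesis during short-term energy deficit". The objectives and hypotheses in B4 do not mention these associations.

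**The concern.** In their standard form, correlation and multiple regression treat rows as independent. Here 20 volunteers x 2 trials gives 40 person-trials, and x 2 legs gives 80 leg-level FSR values, with each whole-body value appearing twice among the 80.

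Dose is also expected to raise both variables. B5.8.1 says "we anticipate observing a mean (SD) difference in muscle FSR of ~0.015 %/h (0.02 %/h) for both the rested and exercised leg" and claims over 95% power for whole-body balance. Two variables that both rise with dose will correlate across doses even if they are unrelated at any given dose.

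At stake is the interpretation of the association that B5.3 puts forward as new. Section B2 says the muscle to whole-body relationship has not been thoroughly examined. It also reports a study in which net balance was higher after 70 g than after 40 g of protein while muscle FSR did not differ. Whether the two move together is therefore an open question, and a correlation produced by dose alone would look like an answer.

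**Working it through.** **1. The plan's own figure.** Standardised FSR effect = 0.015 / 0.02 = 0.75. A two-sided paired t-test at 0.05 (sidedness is not stated) has 77.1% power at n = 15, 80.1% at n = 16 and 88.9% at n = 20. The stated 16 reproduces, and the stated 90% does so to within about one point. So 0.75 is a paired effect, in units of the SD of within-volunteer differences. These figures concern the dose comparison only.

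**2. Whole-body effect.** Its size is not given. With n = 20, 95% power in a paired t-test needs an effect of 0.85, so over 95% power implies at least that. I also use 2.0 as an assumed larger value.

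**3. Dose enters balance by construction.** From the B5.4 equations:

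NB = PS - PB = 25 x (Ra_Phe - hydroxylation) - 25 x (Ra_Phe - F_Phe) + PRO_MEAL = 25 x (F_Phe - hydroxylation) + PRO_MEAL.

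PRO_MEAL is 85% of the EAA ingested, so it differs between trials by 0.85 x (0.30 - 0.10) = 0.17 g/kg. Hydroxylation may offset part of this.

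**4. Expected pooled correlation with no true link.** Let total SD be 1 within a dose and the within-volunteer correlation be ICC. The SD of differences is sqrt(2(1 - ICC)), and a paired effect d shifts the outcome by s = d x sqrt(2(1 - ICC)). Pooled over two doses:

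r = (s_F x s_W / 4) / sqrt[(1 + s_F²/4)(1 + s_W²/4)].

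At ICC 0, s_F = 0.75 x 1.414 = 1.061 and s_W = 0.85 x 1.414 = 1.202, so r = 0.319 / sqrt(1.281 x 1.361) = 0.24. The simulated mean below was 0.243.

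**5. False-positive rate.** I simulated 20 volunteers x 2 doses x 2 legs, 20,000 trials per setting, with no true association. Assumptions not in the documents: ICC 0 to 0.7, a leg shift of 0.75, and half of the residual FSR variance shared by the two legs in a trial. Proportion with p < 0.05:

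| Pooled analysis | ICC 0 | 0.3 | 0.5 | 0.7 |
|---|---|---|---|---|
| 40 rows, whole-body d = 0.85 | 33% | 21% | 16% | 13% |
| 80 rows, whole-body d = 0.85 | 51% | 37% | 30% | 26% |
| 40 rows, whole-body d = 2.0 | 73% | 54% | 36% | 20% |
| 80 rows, whole-body d = 2.0 | 89% | 76% | 58% | 39% |

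Repeating the d = 0.85 case with the leg assumptions varied gives about 12-34% (one leg) and 24-56% (both legs). I quote these wider ranges as the size.

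**6. Separating the two causes, and partial remedies.**

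- No dose effect at all, so repeated rows only: 5-11% (40 rows), 7-24% (80 rows).
- Dose (and leg) adjusted, volunteer ignored: 5-11% (40 rows), 11-25% (80 rows).
- Volunteer adjusted, dose omitted: about 43% (d = 0.85), 78% (d = 2.0).
- Both legs in a mixed model with dose and leg fixed and volunteer as the only random effect: about 8-18% (250 trials per setting, ICC 0.3-0.7, 25-75% of residual variance shared between legs). With volunteer as fixed effects instead: 9-21%. The two legs share one whole-body value, and neither model allows for that.
- Within-volunteer differences, one leg, n = 20: 5%.
- Correlation within one dose and one leg, n = 20: 5%.

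**The case against.** The strongest reply is that the plan never says rows will be pooled. Multiple regression can carry dose as a covariate, and correlations can be run per dose and leg or on change scores, both of which hold 5%. The sample size reproduces only as a paired calculation; a two-sample calculation gives 28 per arm. The authors therefore allowed for pairing there without saying so, and silence in B5.8.2 is weak evidence that they would ignore it for associations. All of this stands. A reader might infer that the planned p-values are wrong; the documents support only that they would be wrong under pooling.

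A reader might also take the associations for a main aim because B5.3 presents them as a first. They are in neither objective and none of the four hypotheses in B4. B5.1 names muscle protein synthesis and whole-body protein balance as the primary outcomes, and B5.8.1 powers only dose comparisons.

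Finally, the documents give neither the ICC nor the whole-body effect, so no single inflation figure can be defended. That is why ranges are shown.

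What remains is that the text admits both valid and seriously invalid analyses and leaves the choice until the data are in hand. The multiplicity adjustment in the same section repairs neither confounding by dose nor dependence between rows.

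**Conclusion.** The concern holds as a conditional one. B5.8.2 does not define the unit of analysis or the handling of dose, leg and volunteer for the associations. If rows are pooled over doses, a nominal 5% test with no true association rejects in roughly 12-34% of trials with one leg and 24-56% with both. This rests on the plan's FSR effect, the minimum whole-body effect implied by its power claim, and an assumed ICC from 0.7 to 0; the rates rise if the whole-body effect is larger. Adjusting for dose alone or volunteer alone is not enough in general. The consequence falls on a secondary, explanatory claim. It would be wrong to conclude that the primary dose comparison is undermined, since that is a separate analysis.

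**What to change.** In B5.8.2, name the outcome pairs and replace the general sentence with a correlation or regression of within-volunteer differences (0.30 minus 0.10 g/kg), separately for each leg, n = 20. This removes both dose and volunteer. In the regression form, treatment sequence can be added to absorb a period effect.

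Alternatively, if both legs are to be analysed together, specify a linear mixed model for FSR with the whole-body measure as predictor, dose, leg and period as fixed effects, and random effects for volunteer and for trial within volunteer. The trial term is essential because both legs share one whole-body value. The two options are not identical: the mixed model combines within- and between-volunteer information, so the plan should say which relationship is meant.

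The cost is one or two sentences and no new data. There are fewer effective observations, so intervals will be wider.
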